	Grade 2	Hold study drug/study regimen dose until resolution to Grade ≤ 1 .	
For Grade 2
 
 – Consult a neurologist. – Consider EMG/NCS – Consider discussing with the Clinical Study Lead, as needed. – Observation for additional symptoms or consider initiating prednisone 0.5–1 mg/kg orally – If progression, initiate methylprednisolone 2–4 mg/kg/day and treat as GBS – Sensory neuropathy/neuropathic pain may be managed by appropriate medications (e.g., gabapentin or duloxetine).
	Grade 3 or 4	
For Grade 3 or 4
 
Permanently discontinue study drug/study regimen.
	
For Grade 3 or 4
 
 – Consider discussing with Clinical Study Lead, as needed. – Recommend hospitalization. – Monitor symptoms and consult a neurologist. – Treat per Guillain-Barré Syndrome recommendations

Guillain-Barré Syndrome (GBS)		General Guidance	
 - Recommend hospitalization - Obtain neurology consult - Obtain MRI of spine to rule out compression lesion - Obtain lumbar puncture - Antibody tests for GBS variants - Pulmonary function tests - Obtain electromyography (EMG) and nerve conduction studies - Frequently monitor pulmonary function tests and neurologic evaluations - Monitor for concurrent autonomic dysfunction - Initiate medication as needed for neuropathic pain
	Grade 2-4	Grade 2-4 Permanently discontinue	Start IVIG or plasmapheresis in addition to methylprednisolone 1 gram daily for 5 days, then taper over 4 weeks.
Myasthenia gravis		General Guidance	
 - Obtain neurology consult - Recommend hospitalization - Obtain pulmonary function tests - Obtain labs: ESR, CRP, creatine phosphokinase (CPK), aldolase and anti-striational antibodies - Consider cardiac exam, ECG, troponin, transthoracic echocardiogram for possible concomitant myocarditis - Obtain electromyography (EMG) and nerve conduction studies - Consider MRI of brain/spine to rule out CNS involvement by disease - Avoid medications that might exacerbate MG (e.g. beta blockers, some antibiotics, IV magnesium)
	Grade 2	Permanently discontinue	
 - Consider pyridostigmine 30mg three times daily and gradually increase based on symptoms (max dose 120mg four times daily) - Consider starting low dose prednisone 20mg daily and increase every 3-5 days. (Target dose 1mg/kg/day. Max dose 100mg daily)

	Grade 3-4	Permanently discontinue	
 - Start methylprednisolone 1-2mg/kg/day. Taper steroids based on symptom improvement - Start plasmapheresis or IVIG - Consider rituximab if refractory to plasmapheresis or IVIG - Frequent PFT assessments - Daily neurologic evaluations
Myocarditis	
Any Grade (Refer to NCI CTCAE applicable version in study protocol for defining the CTCAE grade/severity)
	
General Guidance Discontinue drug permanently if biopsy-proven immune-mediated myocarditis.
	
For Any Grade
 
 - Initial work-up should include clinical evaluation, B-type natriuretic peptide (BNP), cardiac enzymes, electrocardiogram (ECG), echocardiogram (ECHO), monitoring of oxygenation via pulse oximetry (resting and exertion), and additional laboratory work-up as indicated. Spiral CT or cardiac MRI can complement ECHO to assess wall motion abnormalities when needed. - Patients should be thoroughly evaluated to rule out any alternative etiology (e.g., disease progression, other medications, or infections) - The prompt diagnosis of immune-mediated myocarditis is important, particularly in patients with baseline cardiopulmonary disease and reduced cardiac function. - Consider discussing with the Clinical Study Lead, as needed. - Monitor patients for signs and symptoms of myocarditis (new onset or worsening chest pain, arrhythmia, shortness of breath, peripheral edema). As some symptoms can overlap with lung toxicities, simultaneously evaluate for and rule out pulmonary toxicity as well as other causes (e.g., pulmonary embolism, congestive heart failure, malignant pericardial effusion). Consult a cardiologist early, to promptly assess whether and when to complete a cardiac biopsy, including any other diagnostic procedures. - as indicated. Spiral CT or cardiac MRI can complement ECHO to assess wall motion abnormalities when needed.

	Grade 2, 3 or 4	
 If Grade 2-4, permanently discontinue study drug/study regimen. 	
For Grade 2-4
 
 Monitor symptoms daily, hospitalize. Consider cardiology consultation and a prompt start of high-dose/pulse corticosteroid therapy Supportive care (e.g., oxygen). If no improvement consider additional immunosuppressive therapy such as TNF inhibitors (e.g., infliximab), IVIG or plasmapheresis or other therapies depending on the clinical condition of the patient, based on the discretion of the treating specialist consultant or relevant practice guidelines. 
Caution: It is important to rule out sepsis and refer to infliximab label for general guidance before using infliximab. Infliximab is contraindicated for patients who have heart failure.

Myositis/ Polymyositis	
Any Grade
 
(Refer to NCI CTCAE applicable version in study protocol for defining the CTCAE grade/severity)
	General Guidance	
For Any Grade
 
 Patients should be thoroughly evaluated to rule out any alternative etiology (e.g., disease progression, other medications, or infections). Monitor patients for signs and symptoms of poly/myositis. Typically, muscle weakness/pain occurs in proximal muscles including upper arms, thighs, shoulders, hips, neck and back, and; also difficulty breathing and/or trouble swallowing can occur and progress rapidly. Increased general feelings of tiredness and fatigue may occur, and there can be new-onset falling, difficulty getting up from a fall, and trouble climbing stairs, standing up from a seated position, and/or reaching up. If poly/myositis is suspected, a Neurology consultation should be obtained early, with prompt guidance on diagnostic procedures. Myocarditis may co-occur with poly/myositis; refer to guidance under Myocarditis. Given breathing complications, refer to guidance under Pneumonitis/ILD. Given possibility of an existent (but previously unknown) autoimmune disorder, consider Rheumatology consultation.

		
 - Consider, as necessary, discussing with the Clinical Study Lead. - Initial work-up should include clinical evaluation, creatine kinase, aldolase, lactate dehydrogenase (LDH), blood urea nitrogen (BUN)/creatinine, erythrocyte sedimentation rate or C-reactive protein (CRP) level, urine myoglobin, and additional laboratory work-up as indicated, including a number of possible rheumatological/antibody tests (i.e., consider whether a rheumatologist consultation is indicated and could guide need for rheumatoid factor, antinuclear antibody, anti-smooth muscle, antisynthetase [such as anti-Jo-1], and/or signal-recognition particle antibodies). Confirmatory testing may include electromyography, nerve conduction studies, MRI of the muscles, and/or a muscle biopsy. Consider Barium swallow for evaluation of dysphagia or dysphonia.
Grade 1	
 • No dose modifications. 	
For Grade 1
 
 - Monitor and closely follow up in 2 to 4 days for clinical symptoms and initiate evaluation as clinically indicated. - Consider Neurology consult. - Consider, as necessary, discussing with the Clinical Study Lead.
Grade 2	
 • Hold study drug/study regimen dose until resolution to Grade ≤ 1. • Permanently discontinue study drug/study regimen if it does not resolve to Grade ≤ 1 within 30 days or if there are signs of respiratory insufficiency. 	
For Grade 2
 
 - Monitor symptoms daily and consider hospitalization. - Consider Rheumatology or Neurology consult, and initiate evaluation. - Consider, as necessary, discussing with the Clinical Study Lead. - If clinical course is rapidly progressive (particularly if difficulty breathing and/or trouble swallowing), promptly start IV methylprednisolone 2 to 4 mg/kg/day systemic steroids along with receiving input from Neurology consultant - If clinical course is not rapidly progressive, start systemic steroids (e.g., prednisone 1 to 2 mg/kg/day PO or IV equivalent); if no improvement within 2 to

		
3 days, continue additional work up and start treatment with IV methylprednisolone 2 to 4 mg/kg/day
 
 - If after start of IV methylprednisolone at 2 to 4 mg/kg/day there is no improvement within 3 days, consider additional - immunosuppressive therapy such as TNF inhibitors (e.g., infliximab), IVIG or plasmapheresis, or other therapies based on the discretion of the treating specialist consultant or relevant practice guideline Caution: It is important to rule out sepsis and refer to infliximab label for general guidance before using infliximab.
Grade 3	
For Grade 3
 
 - Hold study drug/study regimen dose until resolution to Grade ≤ 1. - Permanently discontinue study drug/study regimen if Grade 3 imAE does not resolve to Grade ≤ 1 within 30 days or if there are signs of respiratory insufficiency. 	
For Grade 3
 
 - Monitor symptoms closely; recommend hospitalization. - Consider Rheumatology and/or Neurology consult - Consider discussing with the Clinical Study Lead, as needed. - Promptly start IV methylprednisolone 2 to 4 mg/kg/day systemic steroids along with receiving input from Neurology consultant. - If after start of IV methylprednisolone at 2 to 4 mg/kg/day there is no improvement within 2 to 3 days, consider starting another immunosuppressive therapy such as a TNF inhibitor (e.g., infliximab at 5 mg/kg IV, may be repeated at 2 and 6 weeks after initial dose at the discretion of the treating provider or relevant practice guidelines). Caution: It is important to rule out sepsis and refer to infliximab label for general guidance before using infliximab. - Consider whether patient may require IV IG, plasmapheresis.
Grade 4	
For Grade 4
 
Permanently discontinue study drug/study regimen.
	
Grade 4
 
 - Monitor symptoms closely; recommend hospitalization. - Consider Rheumatology and/or Neurology consult

			
 - Consider discussing with the Clinical Study Lead, as needed. - Promptly start IV methylprednisolone 2 to 4 mg/kg/day systemic steroids along with receiving input from Neurology consultant. - If after start of IV methylprednisolone at 2 to 4 mg/kg/day there is no improvement within 2 to 3 days, consider starting another immunosuppressive therapy such as a TNF inhibitor (e.g., infliximab at 5 mg/kg IV, may be repeated at 2 and 6 weeks after initial dose at the discretion of the treating provider or relevant practice guidelines). Caution: It is important to rule out sepsis and refer to infliximab label for general guidance before using infliximab.
--	--	--	--

¹ SCAR terms include Stevens-Johnson Syndrome (SJS), Toxic Epidermal Necrolysis (TEN), Erythema Multiforme, Acute Generalized Exanthematous Pustulosis, Drug Reaction with Eosinophilia and Systemic Symptoms (DRESS) and Drug-induced hypersensitivity syndrome.

Other–Immune-Mediated Reactions

Severity Grade of the Event (Refer to NCI CTCAE applicable version in study protocol for defining the CTCAE grade/severity)	Dose Modifications	Toxicity Management
Any Grade	Note: It is possible that events with an inflammatory or immune mediated mechanism could occur in nearly all organs, some of them are not noted specifically in these guidelines (e.g. immune thrombocytopenia, haemolytic anaemia, uveitis, vasculitis).	
 – Patients should be thoroughly evaluated to rule out any alternative etiology (e.g., disease progression, other medications, or infections). – The Clinical Study Lead may be contacted for immune-mediated reactions not listed in the “specific immune-mediated reactions” section – Consultation with relevant specialist – Treat accordingly, as per institutional standard.
Grade 1	No dose modifications.	Monitor as clinically indicated
Grade 2	
 – Hold study drug/study regimen until resolution to ≤ Grade 1 or baseline. – If toxicity worsens, then treat as Grade 3 or Grade 4. – Study drug/study regimen can be resumed once event stabilizes to Grade ≤1 after completion of steroid taper. – Consider whether study drug/study regimen should be permanently discontinued in Grade 2 events with high likelihood for morbidity and/or mortality when they do not rapidly improve to Grade <1 upon treatment with systemic steroids and following full taper 	
For Grade 2, 3, or 4
 
Treat accordingly, as per institutional standard, appropriate clinical practice guidelines, and society guidelines. (See page 4).

Grade 3	Hold study drug/study regimen	
Grade 4	Permanently discontinue study drug/study regimen	

Note: As applicable, for early phase studies, the following sentence may be added: “Any event greater than or equal to Grade 2, please discuss with Clinical Study Lead.”

Infusion-Related Reactions

Severity Grade of the Event (Refer to NCI CTCAE applicable version in study protocol for defining the CTC AE grade/severity)	Dose Modifications	Toxicity Management
Any Grade	General Guidance	For Any Grade
		
 – Manage per institutional standard at the discretion of investigator. – Monitor patients for signs and symptoms of infusion-related reactions (e.g., fever and/or shaking chills, flushing and/or itching, alterations in heart rate and blood pressure, dyspnea or chest discomfort, or skin rashes) and anaphylaxis (e.g., generalized urticaria, angioedema, wheezing, hypotension, or tachycardia).
Grade 1 or 2	For Grade 1	For Grade 1 or 2
	The infusion rate of study drug/study regimen may be decreased by 50% or temporarily interrupted until resolution of the event.	
 – Acetaminophen and/or antihistamines may be administered per institutional standard at the discretion of the investigator. – Consider premedication per institutional standard or study protocol prior to subsequent doses. – Steroids should not be used for routine premedication of Grade ≤ 2 infusion reactions.
	For Grade 2	
	
 – The infusion rate of study drug/study regimen may be decreased 50% or temporarily interrupted until resolution of the event. – Subsequent infusions may be given at 50% of the initial infusion rate. 	
Grade 3 or 4	For Grade 3 or 4	For Grade 3 or 4
	Permanently discontinue study drug/study regimen.	
 – Manage severe infusion-related reactions per institutional standard, appropriate clinical practice guidelines, and society guidelines.

Non-Immune-Mediated Reactions

Severity Grade of the Event (Refer to NCI CTCAE applicable version in study protocol for defining the CTCAE grade/severity)	Dose Modifications	Toxicity Management
Any Grade	Note: Dose modifications are not required for AEs not deemed to be related to study treatment (i.e., events due to underlying disease) or for laboratory abnormalities not deemed to be clinically significant.	Treat accordingly, as per institutional standard.
Grade 1	No dose modifications.	Treat accordingly, as per institutional standard.
Grade 2-3	Hold study drug/study regimen until resolution to \leq Grade 1 or baseline.	Treat accordingly, as per institutional standard.
Grade 4	Discontinue study drug/study regimen (Note: For Grade 4 lab, decision to discontinue should be based on accompanying clinical signs/symptoms, the Investigator's clinical judgment, and consultation with the Sponsor.).	Treat accordingly, as per institutional standard.

Note: As applicable, for early phase studies, the following sentence may be added: "Any event greater than or equal to Grade 2, please discuss with Clinical Study Lead."

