7.3. DOSE MODIFICATION AND DELAYS

7.3.1. GENERAL RULES FOR DOSE MODIFICATION AND DELAYS

- Dose modification (reduction or escalation) is not allowed.
- Dose delays in case of clinically meaningful events are permitted; however, study treatment should be discontinued in case of 4 weeks delays.
- All the response evaluation procedures including CT scans should be performed as planned in patients with treatment delay without regard to the cycles of study treatment. Dose delays, reasons for treatment delay, actions to be taken and outcome will be recorded in patient chart and CRF.
- Regarding the adverse events, dose delays could be made under investigators' discretion.
- When the study treatment is restarted, the investigator should ensure that AE is recovered \leq grade 1 or there is no safety risk for the patients.
- Prophylactic use of G-CSF (or GM-CSF) or erythropoietin is not allowed.

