Based on the severity of the imAE, durvalumab and/or tremelimumab should be withheld and corticosteroids administered. Upon improvement to Grade ≤ 1 , corticosteroid should be tapered over ≥ 28 days. More potent immunosuppressive agents should be considered for events not responding to systemic steroids. Alternative immunosuppressive agents not listed in this guideline may be considered at the discretion of the investigator based on clinical practice and relevant guidelines. With long-term steroid and other immunosuppressive use, consider the need for glucose monitoring.

Dose modifications of study drug/study regimen should be based on severity of treatment-emergent toxicities graded per NCI CTCAE version in the applicable study protocol.

Considerations for Prophylaxis for Long Term use of Steroids for Patients Receiving Immune Checkpoint Inhibitor Immunotherapy

- **Infection Prophylaxis:** Pneumocystis jirovecii pneumonia (PJP), antifungal and Herpes Zoster reactivation
- **Gastritis:** Consider prophylaxis for patients at high risk of gastritis (e.g. NSAID use, anticoagulation) when the patient is taking steroid therapy
- **Osteoporosis:** Consider measures for prevention and mitigation of osteoporosis .

Relevant Society Guidelines for Management of imAEs

These society guidelines are provided as references to serve in support of best clinical practice and the TMGs. Please note, these were the current versions of these guidelines at the time of updating TMGs. Please refer to the most up to date version of these guidelines.

1. Brahmer JR, et al. Society for Immunotherapy of Cancer (SITC) clinical practice guideline on immune checkpoint inhibitor-related adverse events. J Immunother Cancer 2021;9:e002435

2. Brahmer JR, et al. Management of immune-related adverse events in patients treated with immune checkpoint inhibitor therapy: American Society of Clinical Oncology Clinical Practice Guideline. *J Clin Oncol* 2018;36(17):1714-1768.
3. Haanen JBAG, et al. Management of toxicities for immunotherapy: European Society for Medical Oncology (ESMO) clinical practice guidelines for diagnosis, treatment, and follow-up. *Annals Oncol* 2017;28(Suppl4):i119-i1142.
4. Sangro B, et al. Diagnosis and management of toxicities of immune checkpoint inhibitors in hepatocellular carcinoma. *J Hepatol* 2020;72(2):320-341.

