		
investigator, in discussion with AstraZeneca Clinical Study Lead.
 
For patients treated with durvalumab in combination with tremelimumab or tremelimumab monotherapy,
 
Permanently discontinue both durvalumab and tremelimumab for
 
1) Grade 3 diarrhea/colitis or 2) Any grade of intestinal perforation
 
Grade 4
 
Permanently discontinue study drug/study regimen.
	
– If perforation is suspected, consult a surgeon experienced in abdominal surgery immediately without any delay.

Hepatitis
 
Infliximab should not be used for management of immune-related hepatitis.
 
 
PLEASE SEE shaded area immediately below this section to find guidance for management of “Hepatitis (elevated LFTS)” in hepatocellular carcinoma (HCC) patients (or secondary tumour involvement of the liver with abnormal baseline values [BLV])
 
	
Any Grade
 
(Refer to NCI CTCAE applicable version in study protocol for defining the CTCAE grade/severity)
	
General Guidance
	
For Any Grade

	
ALT or AST ≤ 3 x ULN or total bilirubin ≤ 1.5 x ULN
	
 • No dose modifications. • If it worsens, then consider holding therapy. 	
– Continue transaminase and total bilirubin monitoring per protocol.

	
ALT or AST $> 3 \leq 5$ x ULN or total bilirubin $> 1.5 \leq 3$ x ULN
	
 – Hold study drug/study regimen dose until ALT or AST ≤ 3 x ULN or total bilirubin ≤ 1.5 x ULN. Resume study drug/study regimen after completion of steroid taper (<10 mg prednisone or equivalent). – Permanently discontinue study drug/study regimen for any case meeting Hy’s law laboratory criteria (AST or ALT $\geq 3 \times$ ULN AND bilirubin $\geq 2 \times$ ULN without initial 	
 – Regular and frequent checking of transaminases and total bilirubin (e.g., every 1 to 2 days) until transaminases and total bilirubin elevations improve or resolve. – If no resolution to ALT or AST ≤ 3 x ULN or total bilirubin ≤ 1.5 x ULN in 1 to 2 days, consider discussing with Clinical Study Lead, as needed. – If event is persistent (>2 to 3 days) or worsens, promptly start prednisone 1 to 2 mg/kg/day PO or IV equivalent.

		findings of cholestasis (i.e., elevated ALP) and in the absence of any alternative cause.	

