	ALT or AST > 7 X BLV OR > 20 ULN whichever occurs first OR bilirubin > 3ULN	Permanently discontinue study drug/study regimen.	Same as above (except recommend obtaining liver biopsy early)
Nephritis and/or renal dysfunction	Any Grade (Refer to NCI CTCAE applicable version in study protocol for defining the CTCAE grade/severity)	General Guidance	For Any Grade 
 - Patients should be thoroughly evaluated to rule out any alternative etiology (e.g., disease progression, infections, recent IV contrast, medications, fluid status). - Consider Consulting a nephrologist. - Consider imaging studies to rule out any alternative etiology - Monitor for signs and symptoms that may be related to changes in renal function (e.g., routine urinalysis, elevated serum BUN and creatinine, decreased creatinine clearance, electrolyte imbalance, decreased urine output, or proteinuria). Follow urine protein/creatinine ratio every 3-7 days
	Grade 1	No dose modifications.	For Grade 1 
 - Monitor serum creatinine weekly and any accompanying symptoms. 
 • If creatinine returns to baseline, resume regular monitoring per study protocol. • If creatinine worsens, depending on the severity, treat as Grade 2, 3, or 4- - Consider hydration, electrolyte replacement, and diuretics, as clinically indicated. - Consider nephrologist consult if not resolved within 14 days, or earlier as clinically indicated
	Grade 2	Hold study drug/study regimen until resolution to Grade ≤1 or baseline. 
 • If toxicity improves to Grade ≤1 or baseline, then resume study drug/study regimen after completion of steroid taper (<10 mg prednisone, or equivalent). 	For Grade 2 
 - Consider including hydration, electrolyte replacement, and diuretics as clinically indicated - Follow urine protein/creatinine ratio every 3-7 days - Carefully monitor serum creatinine as clinically warranted.

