			
 - Consult nephrologist and consider renal biopsy if clinically indicated. - Start prednisone 0.5 – 1 mg/kg/day if other causes are ruled out - If event is persistent beyond 5 days or worsens, increase to prednisone up to 2 mg/kg/day PO or IV equivalent. - If event is not responsive within 5 days or worsens despite prednisone at 1 to 2 mg/kg/day PO or IV equivalent, consider additional workup. When event returns to baseline, resume study drug/study regimen and routine serum creatinine monitoring per study protocol.
	Grade 3 or 4	Permanently discontinue study drug/study regimen.	
For Grade 3 or 4
 
 - Carefully monitor serum creatinine daily. - Follow urine protein/creatinine ratio every 3-7 days - Consult nephrologist and consider renal biopsy if clinically indicated. - Promptly start prednisone 1 to 2 mg/kg/day PO or IV equivalent. - If event is not responsive within 3 to 5 days of steroids or worsens despite prednisone at 1 to 2 mg/kg/day PO or IV equivalent, consider additional workup and prompt treatment with an immunosuppressant
Rash or Dermatitis (Including Pemphigoid)	Any Grade (Refer to NCI CTCAE applicable version in study protocol for definition of severity/grade depending on type of skin rash)	General Guidance	
For Any Grade
 
 - Patients should be thoroughly evaluated to rule out any alternative etiology. - Monitor for signs and symptoms of dermatitis (rash and pruritus). 
HOLD STUDY DRUG IF GRADE 3 PEMPFIGOID OR SEVERE CUTANEOUS ADVERSE REACTION (SCAR)¹ IS SUSPECTED.
 
 - PERMANENTLY DISCONTINUE STUDY DRUG IF SCAR OR GRADE 3 PEMPFIGOID IS CONFIRMED.

	Grade 1	No dose modifications.	For Grade 1 
 – Consider symptomatic treatment, including oral antipruritics (e.g., diphenhydramine or hydroxyzine) and topical therapy (e.g., emollient, lotion, or institutional standard).

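### Appendix A gives two restart conditions for Grade 2 nephritis, one that waits for the steroid taper and one that does not; the main hepatitis table also joins its limits with a loose *or*

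*Combined protocol and SAP*

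**What the plan says.** **Nephritis, Grade 2 (Appendix A, Specific Immune-Mediated Reactions).**

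- Dose Modifications cell: hold until Grade 1 or lower or baseline, "then resume study drug/study regimen after completion of steroid taper". Completion is glossed as below 10 mg prednisone or equivalent.
- Toxicity Management cell, same row: prednisone is started "if other causes are ruled out" and increased if the event persists or worsens. The cell closes with "When event returns to baseline, resume study drug/study regimen and routine serum creatinine monitoring per study protocol".

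**Taper length (Appendix A, general considerations).** After improvement to Grade 1 or lower, "corticosteroid should be tapered over" 28 days or more.

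**Delay limit (section 7.3.1).** Delays are allowed, but "study treatment should be discontinued in case of 4 weeks delays". Section 7.2 sets dosing every 4 weeks.

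**Hepatitis, unshaded table (Appendix A).**

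- Lowest row: entered when ALT or AST is at most 3 x ULN *or* bilirubin is at most 1.5 x ULN. No dose modification; "If it worsens, then consider holding therapy".
- Second row: entered when ALT or AST is above 3 and up to 5 x ULN *or* bilirubin is above 1.5 and up to 3 x ULN. The instruction begins "Hold study drug/study regimen dose until ALT or AST" and gives the limits as at most 3 x ULN *or* bilirubin at most 1.5 x ULN, with restart after the taper.
- Row for ALT or AST above 5 and up to 10 x ULN: hold, with the same *or* in the limits for resuming.

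**The concern.** The two nephritis cells differ on two things: whether the taper must be finished, and how far the event must have recovered. The row itself starts steroids, so a taper will often be running when the question of restart arises. On the day a patient returns to baseline, one cell says resume and the other says keep holding. A patient who settles at Grade 1 without reaching baseline meets the opposite conflict: once the taper is complete the dose cell allows restart, and the management cell does not.

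In a multicentre trial, two sites could therefore treat the same course differently, and both could cite the appendix. The immediate stake is patient safety. The choice can also decide whether a patient meets the delay limit in section 7.3.1, and so how long that patient is treated.

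In the hepatitis table, the *or* lets a patient with a transaminase rise and normal bilirubin satisfy the no-modification row and a hold row together, and satisfy the release limit when the hold begins.

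**Working it through.** The plan gives no figure to reproduce. The check sets the cells side by side and then works out what the difference means for dose delay.

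**1. Nephritis: does another section settle it?**

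- Section 7.3.1 asks for recovery to Grade 1 or lower, or no safety risk, at restart. It does not mention tapers.
- Section 7.7.1 prohibits systemic corticosteroids above 10 mg/day prednisone or equivalent, which would bar restart on a higher dose.
- Section 7.7.2 permits steroidal agents and treatment of adverse events.

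None of these says which cell applies.

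**2. Nephritis: effect on dose delay.** Let *t* be days from the last dose to onset, *u* days from onset to return to baseline, and *L* days from return to baseline until the taper counts as complete. The next dose is due on day 28.

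- Management cell: restart day = max(28, t + u); delay = restart day − 28.
- Dose cell: restart day = max(28, t + u + L); delay = restart day − 28.

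Assumptions, not in the documents: *t* from 0 to 28, *u* from 5 to 14, and the taper starting at return to baseline. *L* = 28 is the minimum taper in the general considerations. Each entry is the delay in days, management cell / dose cell:

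| t | u = 5 | u = 10 | u = 14 |
|---|---|---|---|
| 0 | 0 / 5 | 0 / 10 | 0 / 14 |
| 7 | 0 / 12 | 0 / 17 | 0 / 21 |
| 14 | 0 / 19 | 0 / 24 | 0 / 28 |
| 21 | 0 / 26 | 3 / 31 | 7 / 35 |
| 28 | 5 / 33 | 10 / 38 | 14 / 42 |

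The management cell gives 0 to 14 days and never reaches 28. The dose cell gives 5 to 42 days and reaches 28 or more in 6 of the 15 combinations, all with later onset or slower recovery.

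In general, the dose cell reaches a 28-day delay when t + u + L ≥ 56, and the management cell when t + u ≥ 56. The choice decides the outcome when 56 − L ≤ t + u < 56. With L = 28 that is 28 ≤ t + u < 56. If the 10 mg gloss were met sooner, say L = 14 (an assumption), it is 42 ≤ t + u < 56, which only the last combination in the table meets (28 + 14 = 42).

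**3. Hepatitis: entry and release conditions applied as printed** (multiples of ULN):

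| ALT and AST | Bilirubin | No-modification row | Hold row, above 3 to 5 | Hold row, above 5 to 10 | Release limit met |
|---|---|---|---|---|---|
| 2 | 0.8 | yes | no | no | yes |
| 4 | 0.8 | yes | yes | no | yes |
| 8 | 0.8 | yes | no | yes | yes |
| 4 | 1.8 | no | yes | no | no |

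The overlap appears when bilirubin is at most 1.5 x ULN and disappears at 1.8. In the second row, steroids start only if the event persists beyond 2 to 3 days or worsens, so the taper condition may have nothing to act on.

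In the shaded table (hepatocellular carcinoma, or liver involvement with abnormal baseline values), isolated rises of 2, 2.5, 3, 5, 6, 7 and 8 times baseline each fall in one row only.

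**The case against.** **Nephritis.** The table has one column for dosing and one for management. The dosing cell states the taper condition, and the management cell can be read as silent on it, not as waiving it. Anyone who follows both cells waits for the taper, and section 7.7.1 points the same way for doses above 10 mg/day. Appendix A also calls itself a recommendation. This harmonised reading is available, but nothing in the text requires it: the management cell gives its own instruction to resume, with its own recovery level, and no order of precedence is stated. The conflict stands.

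**Size.** A reader might infer that a 28-day taper by itself uses up the 4-week limit. It does not. Delay runs from the next due dose, so onset on the dosing day with recovery in 5 days gives a 5-day delay, inside the one-week treatment window in section 8.1. Completion is also glossed as below 10 mg, which may come before day 28. Nor does the management cell mean immediate re-dosing, because the event must first return to baseline.

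**Hepatitis.** This objection largely succeeds. The rows are an escalating ladder. Read literally, ALT at 12 x ULN with normal bilirubin would meet both the no-modification row and the permanent-discontinuation row, which cannot be meant. The second row's management text, on what to do if values have not resolved in 1 to 2 days, presupposes that the release limit is not yet met. The general-guidance cell for this table is empty in the text available, so a convention that the worst row applies may have been lost. What remains is loose drafting, though the same tables do write joint conditions explicitly elsewhere.

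**Conclusion.** The Grade 2 nephritis row gives two restart conditions that differ on the taper and on the recovery level, and no section says which governs. Under the stated assumptions, the delay is 0 to 14 days on one reading and 5 to 42 on the other. The choice of cell can decide whether the section 7.3.1 limit is reached, depending on when in the cycle the event starts, how fast it resolves and how long the taper lasts.

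The hepatitis *or* is secondary. It is ambiguous on its literal wording, in the unshaded table only, and the layout suggests that the overlap is unintended.

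Two stronger readings are tempting and unsupported:

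- A reader might infer that every isolated ALT/AST rise is affected. Patients with liver involvement and abnormal baseline values use the shaded table, where no overlap was found.
- A reader might infer a material effect on the trial's exposure or discontinuation rates. The documents give no frequency for these events, so that cannot be sized. Scans continue on schedule despite delays (sections 7.3.1 and 8.4), so the timing of response assessment is not affected.

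**What to change.** - **Nephritis, Grade 2:** reconcile the two cells so that the row states one restart condition, covering both the recovery level and whether the taper must be complete.
- **Hepatitis, unshaded table:** clarify the *or* so that the entry and release limits refer to the test or tests that triggered the row. If a worst-row convention is intended, state it.

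Which restart rule applies is for the sponsor and the drug supplier's safety group to decide; this review takes no view. The cost is a minor amendment or clarification of Appendix A, which the version history shows has been amended several times.
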